The primary efficacy endpoint of HI-E per IWG (Cheson, 2006) is defined as proportion of subjects meeting HI-E criteria of ≥ 1.5 g/dL increase in Hgb sustained over any consecutive 56-day period in the absence of RBC transfusions from W1D1 through Week 24. Subjects discontinued from the treatment period without achieving HI-E will be counted as non-responders. Dose modification guidance for luspatercept in Section 7.2.2 defines that, if predose Hgb is ≥ 12.0 g/dL at the day of dosing, the dose should be delayed until Hgb is < 11.0 g/dL. For subjects who meet this criterion and then have their dose delayed, if their Hgb levels temporarily decrease to < 1.5 g/dL but achieve ≥ 1.5 g/dL again after treatment resumption, this period (ie, the time from dose delay to achieving a Hgb increase of ≥ 1.5 g/dL again) will be included as the period of sustained Hgb increase of ≥ 1.5 g/dL.

As the primary efficacy analysis, one sample binomial one sided exact test will be performed based on intent-to-treat (ITT) population, to provide p-value (significance level: 0.025). The number and percentage of subjects who achieve the response and 95% confidence interval (CI) will be presented based on the ITT population.

There is no planned interim analysis for this study.

The primary analysis will be performed when all enrolled subjects have completed 24 weeks of treatment or discontinued before 24 weeks.

Additional follow-up analysis for efficacy and safety will be performed when all subjects have been followed for 5 years from the date of the first dose of IP, or 3 years from the last dose (whichever occurs later) during the Post-Treatment Follow-Up Period of the study.

For more details on statistical considerations please refer to Section 9 of the protocol.

TABLE OF CONTENTS

TITLE PAGE	1
PROTOCOL SUMMARY	6
TABLE OF CONTENTS	12
LIST OF TABLES	18
LIST OF FIGURES	19
1. INTRODUCTION	20
1.1. Myelodysplastic Syndromes	20
1.1.1. Current Treatment Options for Lower Risk MDS.....	21
1.1.1.1. Erythropoiesis Stimulating Agents.....	21
1.1.1.2. Red Blood Cell Transfusions	22
1.1.1.3. Lenalidomide.....	23
1.1.1.4. Hypomethylating Agents	23
1.2. Luspatercept Background	23
1.2.1. Mechanism of Action	23
1.2.2. Nonclinical Studies with Luspatercept	25
1.2.3. Summary of Clinical Experience	25
1.2.3.1. Potential Risks of Human Use	26
1.2.3.2. Overall Benefit Risk Assessment	27
1.3. Rationale	27
1.3.1. Study Rationale and Purpose	27
1.3.2. Rationale for the Study Design	28

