1.3.2.2. Rationale for Study Endpoints

The primary endpoint of HI-E is defined per IWG ([Cheson, 2006](#)) as the proportion of subjects achieving ≥ 1.5 g/dL increase in Hgb over any consecutive 56-day period in the absence of RBC transfusions and reflects the direct clinical benefit of the treatment in lower risk MDS subjects who are not requiring RBC transfusion because the therapeutic goal in this population is to increase Hgb level and prevent subjects from becoming RBC-TD.

While HI-E based on the IWG 2006 criteria is standard hematologic response criteria in lower-risk MDS, difficulties in interpretation of the criteria were reported in the EPOANE3021 Phase 3 study for epoetin alfa, in particular in the subjects who had to transiently discontinue the study treatment due to a rapid/excessive rise in Hgb level, and therefore often had responses of less than 8 week durations (due to drug interruption). To address these difficulties, an ad hoc analysis of erythroid response was conducted by adding some conditions including the condition of “patients with an increase in Hgb level by at least 1.5 g/dL lasting less than 8 weeks due to epoetin alfa discontinuation were considered responders if, when restarting epoetin alfa at lower dose, Hgb still increased by at least 1.5 g/dL” ([Fenaux, 2016](#); [Fenaux, 2018a](#)). Recently, this undesired effect of dosing interruption on HI-E evaluation was also discussed in the IWG and modification of the criteria was suggested, which further supports the importance of addressing the effect of dosing interruption to avoid misinterpretation of HI-E outcome ([Platzbecker, 2019](#); [Platzbecker, 2020](#)). Similar to epoetin alfa, the undesired effects of dosing interruption due to predose Hgb ≥ 12.0 g/dL on HI-E assessment is also expected in luspatercept treatment, especially for lower risk MDS patients who are not requiring RBC transfusion. Therefore, in this ACE-536-MDS-003 study, for subjects who have a dose delay meeting the dose interruption criterion of predose Hgb ≥ 12.0 g/dL, if their Hgb levels temporarily decrease to < 1.5 g/dL but achieve ≥ 1.5 g/dL again after treatment resumption, this period (ie, the time from dose delay to achieving a Hgb increase of ≥ 1.5 g/dL again) will be included as the period of sustained Hgb increase of ≥ 1.5 g/dL for HI-E evaluation.

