5. TABLE OF EVENTS

Table 3: Table of Events

	Screening	Treatment Period								Post-treatment Follow-up			
							Efficacy Assessment Independent of any dose delays						
Section	Day -35 to -1	W1D1 Visit	W2D1 Visit	W3D1 Visit	3-wkly Visits W4D1 W7D1 W10D1 etc.	Other Visits	24-Wk MDS Assessment Visit D169	Every 24 wks D337 D505 etc.	EOT Visit ^a	42-Day Follow-up	Long Term Follow-up	End of Study	
Section										6.2.2/11.1	6.3.1	6.3.2	11.2
Time window				±2 days	±2 days	±2 days	±2 days	±14days ^b	±14days ^b		+2 days	±7 days	

Note:

Weekly visits as displayed above represent visits as they are scheduled if dosing occurs without any dose delays. In the event of dose delays (eg, due to adverse events) the next dosing visit (every 3 weeks for luspatercept) and associated assessments should be delayed accordingly. Assessments to monitor the condition of the subject should be recorded as unscheduled visits. Please note that efficacy assessments (MDS Disease assessments) always occur at the designated days after W1D1 as indicated above. Dose delays do not affect the timing of these assessments.

Informed Consent	6.1	X	–	–	–	–	–	–	–	–	–	–	–
Inclusion/Exclusion Evaluation	6.1	X	–	–	–	–	–	–	–	–	–	–	–
Physical Examination	6.1.5	X	–	–	–	–	–	X	X	X	–	–	–
Demographics	6.1.3	X	–	–	–	–	–	–	–	–	–	–	–
Medical History	6.1.4	X	–	–	–	–	–	–	–	–	–	–	–
HIV and Hep B/C Status	6.1.4.1	X	–	–	–	–	–	–	–	–	–	–	–
Prior RBC and Platelet Transfusions	6.1.2	X	–	–	–	–	–	–	–	–	–	–	–

Table 3: Table of Events (Continued)

		Screening	Treatment Period							Post-treatment Follow-up			
								Efficacy Assessment Independent of any dose delays					
Section	Day -35 to -1	W1D1 Visit	W2D1 Visit	W3D1 Visit	3-wkly Visits W4D1 W7D1 W10D1 etc.	Other Visits	24-Wk MDS Assessment Visit D169	Every 24 wks D337 D505 etc.	EOT Visit ^a	42-Day Follow-up	Long Term Follow-up	End of Study	
Section										6.2.2/11.1	6.3.1	6.3.2	11.2
Time window				±2 days	±2 days	±2 days	±2 days	±14days ^b	±14days ^b		+2 days	±7 days	
INVESTIGATIONAL PRODUCT (IP)													
IP Administration and Accountability Luspatercept	7	—	X	—	—	X	—	—	—	—	—	—	
SAFETY ASSESSMENTS													
ECOG Performance Status	6.1.7	X	X	—	—	X	—	X	X	X	—	—	
Urinalysis	6.1.13	X	X	—	—	Every 12 weeks ie, W13D1, W25D1, etc.	—	—	—	—	—	—	
ECG (12-lead)	6.1.8	X	—	—	—	—	—	—	—	—	—	—	
Pregnancy Test and Counseling	6.1.14	X	X	—	—	X	—	—	—	X	—	—	

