Δ Hgb > 2.0 g/dL (not influenced by RBC transfusions ^d) compared to pre-dose Hgb of the previous luspatercept administration	Reduce dose by one dose level according to Table 4
Predose Hgb ≥ 12.0 g/dL	Dose delay until Hgb < 11.0 g/dL ^d
$\geq 50\%$ increase in white blood cell count (WBC) compared to pre-dose WBC of previous treatment cycle and above upper limit of normal in the absence of an associated condition (eg, infection or concomitant corticosteroid use)	
Dose delay; recheck complete blood count (CBC), including WBC, at least weekly during dose delay. Treatment may be resumed if:
 
WBC values below upper limit of normal^e within 2 weeks
 
If WBC remains above upper limit of normal^e for ≥ 2 consecutive weeks in absence of an associated condition (eg, infection or concomitant corticosteroid use); continue dose delay and collect bone marrow/peripheral blood samples to assess MDS disease status.
 
Treatment may be resumed if:
 
Absence of disease progression per IWG response criteria for altering natural history of MDS (Cheson, 2006) (Appendix E)
 
AND
 
WBC values return below upper limit of normal
 
Discontinue treatment if:
 
Disease progression per IWG response criteria for altering natural history of MDS (Cheson, 2006) (Appendix E)
 
OR
 
WBC remain above upper limit of normal^e

Table 5: Luspatercept Dose Modification: Dose Delay, Dose Reduction, and Discontinuation Guidelines (Continued)

Event at the Day of Dosing (Assessed prior to each IP administration at the respective visit ⁱ)	Action
Presence of $\geq 1\%$ blasts in peripheral blood (based on either local or central laboratory hematology sample)	
Dose interruption; immediately prepare peripheral blood smear^{f,g} for cytromorphology assessment by central pathology laboratory.
 
 • If central pathology laboratory cytromorphology assessment confirms $\geq 1\%$ blasts in the peripheral blood; discontinue treatment^h • If central pathology laboratory cytromorphology assessment determines $< 1\%$ peripheral blasts are present, repeat hematology assessment. 
 – If presence of $< 1\%$ blasts in peripheral blood, treatment can be resumed at next scheduled luspatercept administration. – If presence of $\geq 1\%$ blasts in peripheral blood; discontinue treatment^h

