9.6. Efficacy Analysis

9.6.1. Primary Efficacy Analysis

The primary efficacy endpoint of HI-E per IWG ([Cheson, 2006](#)) within 24 weeks is defined as proportion of subjects meeting HI-E criteria of ≥ 1.5 g/dL increase in Hgb sustained over any consecutive 56-day period in the absence of RBC transfusions from W1D1 through Week 24. Subjects discontinued from the Treatment Period without achieving HI-E will be counted as non-responders.

As the primary efficacy analysis, one sample binomial one sided exact test will be performed based on ITT population, to provide p-value (significance level: 0.025). The statistical hypothesis will be as follows,

$$H_0: p \leq 10\%,$$

$$H_a: p > 10\%$$

where p denotes the true response rate. The number and percentage of subjects who achieve the response and 95% CI will be presented based on the ITT population.

Dose modification guidance for luspatercept in Section [7.2.2](#) defines that, if predose Hgb is ≥ 12.0 g/dL at the day of dosing, the dose should be delayed until Hgb is < 11.0 g/dL. For subjects who meet this criterion and then have their dose delayed, if their Hgb levels temporarily decrease to < 1.5 g/dL but achieve ≥ 1.5 g/dL again after treatment resumption, this period (ie, the time from dose delay to achieving a Hgb increase of ≥ 1.5 g/dL again) will be included as the period of sustained Hgb increase of ≥ 1.5 g/dL. As a sensitivity analysis, the analysis results not applicable to this rule will also be calculated.

Additional details will be outlined in the SAP.

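### Does the uncapped dose-delay credit in the primary HI-E definition need a maximum length?

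*Combined protocol and SAP*

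**What the plan says.** The primary endpoint in Section 9.6.1 is a rise in Hgb of at least 1.5 g/dL sustained over any 56 consecutive days without RBC transfusion, from W1D1 through Week 24. The dose-delay rule applies to subjects held because predose Hgb reached 12.0 g/dL, "if their Hgb levels temporarily decrease to < 1.5 g/dL but achieve ≥ 1.5 g/dL again after treatment resumption". For them, "this period (ie, the time from dose delay to achieving a Hgb increase of ≥ 1.5 g/dL again) will be included as" time in sustained response. The Protocol Summary and Section 1.3.2.2 state the same rule, and Section 9.6.2 repeats it for the secondary analyses. None of these places gives a maximum length or defines *temporarily*.

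In Table 5 (Section 7.2.2) the hold ends on a level, not a time: "Dose delay until Hgb < 11.0 g/dL". Footnote d asks for weekly Hgb checks during the delay. The 12-week limit in footnote c is marked on the row for related adverse events of Grade 3 or higher. The note to Table 3 says that after a delay "the next dosing visit (every 3 weeks for luspatercept) and associated assessments should be delayed accordingly".

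Section 1.3.2.2 gives the reason for the rule. In the epoetin alfa Phase 3 study, subjects interrupted for a rapid or excessive Hgb rise "often had responses of less than 8 week durations (due to drug interruption"). In that study's ad hoc analysis, subjects with a rise "lasting less than 8 weeks due to epoetin alfa discontinuation were considered responders if" Hgb again rose by at least 1.5 g/dL on restarting at a lower dose.

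Section 9.6.1 also prespecifies a sensitivity analysis without the rule and closes with "Additional details will be outlined in the SAP". The combined document contains no SAP text beyond Section 9.

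**The concern.** The credit runs through the hold and then on after dosing resumes, until a reading is again 1.5 g/dL above baseline. A subject back on drug and below threshold for several visits keeps accruing response time. If the interval reaches 56 days, the value that triggered the hold and one later value at +1.5 are enough to make a primary responder. That seems to go further than stopping a mandated interruption from breaking a response.

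The stakes look high because the study is small and single-arm. The primary test uses the rule, there is no control group to absorb a lenient definition, and one subject can decide success. The 10% null also comes from a darbepoetin study whose HI-E definition, as described in Sections 1.1.1.1 and 1.3.2.2, has no such credit.

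**Working it through.** **The plan's own figure.** Inputs from Section 9.3: n = 20, null 10%, expected 45%, one-sided alpha 0.025. Exact binomial tails:

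- P(X ≥ 5 | 0.10) = 0.0432, which fails.
- P(X ≥ 6 | 0.10) = 0.0113, which passes. Success needs 6/20.
- P(X ≥ 6 | 0.45) = 0.945, which agrees with the stated 95%.

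**Can one interval reach 56 days?** With weekly checks during a hold and 3-weekly visits afterwards, the nominal interval is 7h + 21j days. Here h is the number of weeks held and j is the visit after resumption at which the rise is regained.

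| First hold (day) | Days left to Day 168 | Longest 7h + 21j that fits |
|---|---|---|
| 22 | 146 | 140 |
| 43 | 125 | 119 |
| 64 | 104 | 98 |
| 85 | 83 | 77 |
| 106 | 62 | 56 |
| 127 | 41 | below 56 |

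So it can, from five dosing visits. Footnote c would not prevent it even if it applied to Hgb holds: 12 weeks is 84 days, more than 56, and it limits the hold rather than the recovery time.

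**What would a cap do?** Suppose an interval longer than the cap earns no credit, and the rise is regained at the first visit after resumption (j = 1).

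- 42-day cap: 7h + 21 ≤ 42 gives h ≤ 3, so a hold of 4 weeks or more loses all credit.
- 49-day cap: 7h + 21 ≤ 49 gives h ≤ 4, so a hold of 5 weeks or more loses all credit.

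A long hold means Hgb stayed at or above 11.0 g/dL off drug for a long time. Two constructed subjects, both with baseline 9.8 g/dL, show the conflict (rises in g/dL):

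- *Weak, slow recovery.* D8 +0.3, D15 +0.6, D22 +1.0, D43 +2.2 (held), D50 +1.3, D57 +0.9 (re-dosed), D78 +0.7, D99 +0.9, D120 +1.6, D141 +1.1, D162 +0.8. The credited interval is 120 − 43 = 77 days, of which 120 − 57 = 63 follow resumption. Two of 11 readings reach +1.5.
- *Durable response.* D22 +1.2, D43 +2.6 (held), D50 +2.5, D57 +2.3, D64 +2.1, D71 +1.9, D78 +1.7, D85 +1.4, D92 +1.1 (re-dosed), D113 +1.7, D134 +1.4, D155 +1.2. The credited interval is 113 − 43 = 70 days, and 7 of its 9 readings are at threshold.

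| Analysis | Weak | Durable |
|---|---|---|
| Primary rule | responder (77 days) | responder (70 days) |
| 42- or 49-day cap | non-responder | non-responder (observed run D43–D78, 35 days) |
| Without the rule | non-responder | non-responder |
| mHI-E, 56-day mean rise | at most 1.35: not met | D43–D98: 15.6/8 = 1.95: met |

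For these two subjects the cap does no better than the analysis without the rule. Modified HI-E tells them apart.

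**Bracketing.** A cap only removes credit, and an interval above it is treated as in the analysis without the rule. Hence responders without the rule ≤ responders with any cap ≤ responders under the primary rule. If both ends are at least 6, or both are below 6, every cap gives the same conclusion. If they straddle 6, the planned output shows it.

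**Effect on the error rate.** The documents give no rate of rule-only responders, so the range below is assumed. With a strict rate of 10% plus an added share d, P(X ≥ 6) is 0.0113 (d = 0), 0.0241 (d = 1.8 points), 0.026 (2 points), 0.067 (5 points) and 0.196 (10 points). The gap between the actual size of 0.0113 and 0.025 absorbs almost 2 points.

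**Cost of a cap.** If it lowered the true rate from 45% to 43% or 40% (assumptions), power would go from 0.945 to 0.922 or 0.874.

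**The case for a change.** The strongest case for a change is that sensitivity analyses do not alter the primary p-value, which uses the uncapped rule. The analysis without the rule removes all hold credit, so by itself it cannot separate reasonable from excessive credit. A limit on the credit is part of the endpoint definition, and in a single-arm study it is best fixed before responses are known. For a subject with baseline 9.5 g/dL or more, re-dosing below 11.0 always means a rise below 1.5, so passing below threshold after a hold is routine.

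Parts of this stand. The text has no limit, credit after resumption goes beyond the hold itself, and the null was set from a definition without it. But the same routine dip is why the sponsor wrote the rule, and the epoetin alfa condition quoted in Section 1.3.2.2 shows no maximum either. As quoted, that condition is the looser one: it asks only for a renewed rise, whereas here credited and observed time together must still reach 56 days. That section says other conditions existed, so the comparison is limited to what is quoted.

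The flip from 5/20 to 6/20 would follow from any one-subject classification choice at this sample size. It is not evidence against this rule in particular. A hold also requires Hgb to climb more than 2.0 g/dL from a baseline below 10.0, which should be uncommon with an ineffective drug.

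**Conclusion.** No change to the plan follows. The missing maximum is real, and an interval of 56 days or more is feasible after a first hold on Days 22 to 106. Crediting the interval is nevertheless a deliberate and explained choice, and a cap is a trade-off rather than a correction. It would strip credit from holds of four or five weeks and longer, its length would be arbitrary, and it could cost up to about 7 points of power (0.945 − 0.874) under the assumed fall to 40%. The planned analysis without the rule already gives the lower bound for any cap, and mHI-E shows whether the observed mean rise supports the classification.

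What remains does not change a result. The meaning of *temporarily* is a detail that analysts can settle in the SAP. Listing rule-only responders is ordinary reporting. The reference to Hgb levels below 1.5 g/dL is a clerical slip for the increase from baseline, as the end of the same sentence makes clear.

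This conclusion rests on three assumptions: mHI-E is computed from observed values without the credit, the sensitivity analysis is reported beside the primary result, and rule-only responders are uncommon when the drug does not work. The documents neither confirm nor contradict the last of these. The two profiles show what the rule and a cap can do, not how often.

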9.6.2. Secondary Efficacy Analyses

The secondary variables will be analyzed descriptively, unless otherwise specified, and will be based on the ITT population and EE population. Kaplan-Meier methods will be used to estimate curves for time to event secondary variables. Counts and percentages will be used to describe categorical variables. Response rate of HI-E per IWG ([Cheson, 2006](#)) within 24 weeks, based on the EE population, will be analyzed as a secondary endpoint.

Modified hematologic improvement - erythroid (mHI-E) per IWG ([Cheson, 2006](#)) is defined as proportion of subjects meeting mHI-E criteria of ≥ 1.5 g/dL mean increase in Hgb compared to baseline that is sustained over any consecutive 56-day period in the absence of RBC

transfusions from W1D1 through Week 24 (and W1D1 through Week 48) of the Treatment Period. Subjects discontinued from the Treatment Period without achieving a mean Hgb increase ≥ 1.5 g/dL will be counted as non-responders.

HI-E per IWG (Cheson, 2006) within 48 weeks is defined as proportion of subjects meeting HI-E criteria of ≥ 1.5 g/dL increase in Hgb sustained over any consecutive 56-day period in the absence of RBC transfusions from W1D1 through Week 48 of the Treatment Period. Subjects discontinued from the Treatment Period without achieving HI-E will be counted as non-responders.

For subjects who have a dose delay meeting the dose modification criterion described in Section 9.6.1, if their Hgb levels temporarily decrease to < 1.5 g/dL but achieve ≥ 1.5 g/dL again after treatment resumption, this period (ie, the time from dose delay to achieving a Hgb increase of ≥ 1.5 g/dL again) will be included as the period of sustained Hgb increase of ≥ 1.5 g/dL.

Time to HI-E will be summarized only for subjects who achieve HI-E. It is defined as time from W1D1 to first onset of achieving ≥ 1.5 g/dL increase in Hgb over any consecutive 56-day period in the absence of RBC transfusions. It will be summarized separately for subjects who achieve HI-E within the first 24 weeks and 48 weeks from W1D1, respectively.

Time to mHI-E will be summarized only for subjects who achieve mHI-E. It is defined as the time from W1D1 to first onset of achieving ≥ 1.5 g/dL mean increase in Hgb over any consecutive 56-day period in the absence of RBC transfusions. It will be summarized separately for subjects who achieve mHI-E within the first 24 weeks and 48 weeks from W1D1, respectively.

Duration of HI-E will be determined only for subjects who achieve HI-E during the Treatment Period. Duration of HI-E is defined as the maximum duration of achieving ≥ 1.5 g/dL increase in Hgb for subjects who achieve Hgb increase ≥ 56 days in the absence of RBC transfusions. Subjects who maintain HI-E through the end of the Treatment Period or time of analysis will be censored at the date of treatment discontinuation/time of analysis or death, whichever occurs first.

Duration of mHI-E will be determined only for subjects who achieve mHI-E during the Treatment Period. Duration of mHI-E is defined as the maximum duration of achieving ≥ 1.5 g/dL mean increase in Hgb for subjects who achieve a mean Hgb increase of ≥ 56 days in the absence of RBC transfusions. Subjects who maintain mHI-E through the end of the Treatment Period or time of analysis will be censored at the date of treatment discontinuation/time of analysis or death, whichever occurs first.

Proportion of subjects who maintain RBC-TI is defined as proportion of subjects not being given any RBC transfusion during the Treatment Period and will be calculated at Week 24, Week 48, and Week 72.

Time to progression to AML is defined as the time between W1D1 and first diagnosis of AML as per WHO classification of $\geq 20\%$ blasts in peripheral blood or bone marrow. Subjects with diagnosis of AML will be considered to have had an event. Subjects who have not progressed to AML at the time of analysis will be censored at the last assessment date which does not indicate progression to AML.

Overall survival (OS) is defined as the time between W1D1 and death/censored date. Subjects who die, regardless of the cause of death, will be considered to have had an event. Subjects who are alive at the time of analysis will be censored at the last assessment date at which the subject was known to be alive. All subjects who were lost to follow-up will also be censored at the time of last contact.

Full analysis details will be included in the SAP.

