6.1.20. Monitoring for Progression to AML and Other Malignancies/Pre-malignancies

Progression to AML as per WHO classification (Arber, 2016) will be monitored and will be included as part of the safety assessment throughout the course of the study. Progression to AML should be monitored from time of signing of informed consent through 5 years from the date of the first dose of IP, or 3 years from the last dose (whichever occurs later), or until death, lost to follow-up or withdrawal of consent from the study. For that purpose, subjects will be followed post-treatment every 12 weeks for 3 years from the date of last dose of IP and every 6 months thereafter, if applicable.

The occurrence of a new malignancy or pre-malignant lesion will be monitored as an event of interest and should be included as part of the assessment of AEs throughout the course of the study (please refer to Section 10.5 for details). Investigators are to report the development of any new malignancy or pre-malignant lesion as a serious adverse event (SAE), regardless of causal relationship to IP (luspatercept or epoetin alfa), occurring at any time for the duration of the study, from the time of signing the ICF for up to and including long-term follow-up (ie, 5 years from the date of the first dose of IP, or 3 years from the last dose [whichever occurs later]), or until death, lost to follow-up, or withdrawal of consent for further data collection.

Documentation supporting the diagnosis of progression to AML and other malignancies/pre-malignancies (eg, confirmatory histology or cytology results, etc.) may be requested.

Appropriate information related to the diagnosis of AML and other malignancies/pre-malignancies should be captured on the eCRF and in the subject's source documents.

Refer to Section 10.5 and Section 10.6 for more information regarding reporting requirements.

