9.2. Study Population Definitions

Study populations to be analyzed are defined as follows:

Intent-to-treat (ITT): The ITT population will consist of all enrolled subjects regardless of whether or not the subject received IP.

Efficacy Evaluable (EE): The EE population will consist of 1) all subjects who received at least one dose of IP and 2) have at least two hemoglobin assessments \geq 8 weeks apart post-treatment.

Safety: The safety population will consist of all subjects who were enrolled and received at least one dose of IP. Statistical methods to handle missing data will be described in the statistical analysis plan (SAP). The SAP will describe any predefined rules for including/excluding any subjects with data from any analyses (eg, time windows, visit by visit analysis, endpoint analysis, protocol violation).

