9.3. Sample Size and Power Considerations

For the primary efficacy endpoint, HI-E, the sample size is based on one sample binomial exact test. The null hypothesis to be tested is that the proportion of subjects achieving HI-E (defined as ≥ 1.5 g/dL increase in Hgb over any consecutive 56-day period in the absence of RBC transfusions) is $\leq 10\%$; the alternative hypothesis is that the proportion of subjects achieving HI-E is $> 10\%$. With these hypotheses, a sample size of 20 subjects are required with a power of 95% at a one-sided 0.025 alpha level if the expected proportion is 45%. This criterion requires that the lower limit of the 95% confidence intervals for the HI-E rate is greater than 10%.

The selection of a null hypothesis of 10% HI-E rate is based on the results of ARCADE Phase 3 study of darbepoetin, where the proportion of subjects achieving HI-E was reported as 14.7% (95% CI: 8%–25%) (11/75) ([Platzbecker, 2017c](#)). Based on the lower limit of 95% CI, the null hypothesis is assumed as 10%. The expected proportion of 45% HI-E rate is based on the preliminary efficacy observed with luspatercept in the ex-Japan Phase 2 study ([Platzbecker, 2017a](#)). In the study, HI-E rate was 63% (95% CI: 48%–76%) (32/51 evaluable). Based on the lower limit of 95% CI, the expected proportion is assumed as 45%.

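### The EE population requires about eight weeks of post-dose hemoglobin follow-up, so its OS and time-to-AML curves from W1D1 leave out early events, and its HI-E rate drops essentially only non-responders

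*Combined protocol and SAP*

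**What the plan says.** - **Section 9.2** defines ITT as everyone enrolled, dosed or not. EE consists of "all subjects who received at least one dose of IP and 2) have at least two hemoglobin assessments" at least 8 weeks apart, described as post-treatment. The safety population is everyone enrolled and dosed.
- **Section 9.6.2** sets the populations for the secondary efficacy variables: "The secondary variables will be analyzed descriptively, unless otherwise specified, and will be based on the ITT population and EE population". It also names the EE rate of HI-E within 24 weeks as a secondary endpoint.
- **The same section** starts both long-term clocks at first dose: "Overall survival (OS) is defined as the time between W1D1 and death/censored date" and "Time to progression to AML is defined as the time between W1D1 and first diagnosis of AML". It gives no landmark and no separate population for either.
- **Section 6.1.20** says of AML progression that it "will be included as part of the safety assessment throughout the course of the study". Section 9.7 places safety analyses in the safety population.
- **Section 9.6.1** keeps the primary test in ITT ("one sample binomial one sided exact test will be performed based on ITT population") and counts a subject who discontinues without HI-E as a non-responder.
- **Section 9.3** adds that meeting the criterion means a lower 95% confidence limit above 10%.

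**The concern.** EE membership is decided by what happens after the first dose, while OS and time to AML are counted from the first dose. The opening weeks are therefore guaranteed survival time for anyone in EE. A death in that stretch does not count against the EE curve, because the subject is removed from it.

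The response rate has a related problem. A subject with HI-E has, almost by definition, hemoglobin values spanning 56 days and so qualifies for EE. Those who fail to qualify are essentially non-responders. EE thus undoes the Section 9.6.1 rule that stopping early without a response is a failure.

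At stake is how the supportive tables read: an EE survival curve that starts with a flat 100% stretch, an AML curve that may omit early cases of what the protocol treats as a safety outcome, and an EE response rate that could sit above 10% when the ITT rate does not.

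**Working it through.** **1. The plan's own figure.** Section 9.3: "a sample size of 20 subjects are required with a power of 95% at a one-sided 0.025 alpha level if the expected proportion is 45" per cent. On the null rate: "Based on the lower limit of 95% CI, the null hypothesis is assumed as 10" per cent. With n = 20, the smallest r with P(X ≥ r | 0.10) ≤ 0.025 is r = 6:
- r = 5: P = 0.0432, too large.
- r = 6: P = 0.0113; power P(X ≥ 6 | 0.45) = 0.9447.

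That is 94.5% against the stated 95%, so the figure is reproduced. This ITT test does not depend on EE.

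**2. Earliest entry to EE.** I read *post-treatment* as after the first dose. The first scheduled hemoglobin after dosing is W2D1, Day 8. Adding 56 days gives Day 64, which is nominally W10D1. With the ±2-day visit windows those two visits can be 62 − 10 = 52 to 66 − 6 = 60 days apart, so some subjects would need a later value. The earliest qualifying day from scheduled visits is Day 6 + 56 = Day 62.

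**3. Survival at about week 9.** With d early deaths among 20 and no earlier censoring, ITT survival is (20 − d)/20. EE survival is 100% whatever d is.

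| Early deaths | ITT | EE |
|---|---|---|
| 1 | 95% | 100% |
| 2 | 90% | 100% |
| 3 | 85% | 100% |

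**4. How many early deaths to expect.** Appendix C gives median survival of 8.8, 5.3 and 3.0 years for very low, low and intermediate risk. Assuming a constant hazard, the expected number by Day 64 (64/365.25 = 0.175 years) is 20 × (1 − 2^(−0.175/median)):
- 8.8 years: 20 × 0.0137 = 0.27
- 5.3 years: 20 × 0.0227 = 0.45
- 3.0 years: 20 × 0.0397 = 0.79

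For AML, Appendix C gives 10.8 years (low) and 3.2 years (intermediate) to 25% evolution. The expected number is 20 × (1 − 0.75^(0.175/time)): 0.09 and 0.31. For very low risk this time is not reached.

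**5. HI-E rate.** The documents give no dropout rate, so I assume k = 0 to 5 non-responders fail the EE condition. The rate is r/(20 − k), with the exact one-sided tail at 10% and the Clopper-Pearson lower 95% limit.

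| Responders | k | Rate | p | Lower limit |
|---|---|---|---|---|
| 5 | 0 | 5/20 = 25.0% | 0.0432 | 8.7% |
| 5 | 1 | 5/19 = 26.3% | 0.0352 | 9.1% |
| 5 | 2 | 5/18 = 27.8% | 0.0282 | 9.7% |
| 5 | 3 | 5/17 = 29.4% | 0.0221 | 10.3% |
| 6 | 0 | 6/20 = 30.0% | 0.0113 | 11.9% |
| 6 | 5 | 6/15 = 40.0% | 0.0022 | 16.3% |

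With five responders, the lower limit passes 10% only once three non-responders are removed.

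**6. The word *post-treatment*.** In Sections 3.1 and 6.3 the term names the follow-up period after treatment ends. Read that way in Section 9.2, EE would need two hemoglobin values at least 8 weeks apart after the last dose. As far as Table 3 can be read, no such pair is scheduled.

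**The case against.** The strongest reply is that little rests on EE. Every secondary efficacy variable is also planned in ITT, the secondary analyses are descriptive, no EE test is specified, and the primary inference is ITT only. Section 9.5 tabulates population allocation, so removals would be visible. All of this stands, and it keeps the point to supportive tables.

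For HI-E, an evaluable set is defensible. Both planning rates in Section 9.3 rest on evaluable denominators (11 of 75, as Section 1.1.1.1 makes clear, and 32 of 51), and an 8-week condition suits a 56-day endpoint. This also stands. It is why the EE rate can stay, labelled for what it is. The 5/17 example is moreover a selected one. Exactly five responders has probability 0.9811 − 0.9447 = 3.6% at the planned 45%, and three removals are needed as well.

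Four stronger readings are tempting, and the documents do not support them.
- *All early AML is excluded by construction.* Section 9.2 does not require a subject to be AML-free or on treatment. A subject diagnosed early who still gives a later hemoglobin value stays in EE, and Section 6.4.1 collects pre-transfusion values until 8 weeks after the last dose or the EOT visit, whichever is later. Exclusion follows only if hemoglobin data stop. That is plausible, because Section 11.1 lists disease progression as a reason to discontinue, but it is not automatic.
- *RBC-TI is biased in the same direction.* Section 9.6.2 has no rule making discontinuation a failure for RBC-TI. An untransfused early stopper may count as a success, and removing such subjects lowers the rate: for illustration, 15/20 = 75% becomes 12/17 = 71%.
- *All secondary variables are affected.* Time to and duration of response are restricted to responders, so EE and ITT essentially agree. Safety analyses use the safety population.
- *The EE response rate can never fall below ITT.* Boundary cases exist: an inclusive 56-day window can end on values 55 days apart, and an mHI-E mean can use values spanning less than 56 days.

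**Conclusion.** The point holds in a limited form. Leaving early deaths, and early AML cases whose sampling stops, out of a curve that starts at W1D1 can only raise that curve or leave it equal to ITT. EE survival is fixed at 100% to about Day 64 whatever the drug does. Other subjects removed from EE, alive and event-free but no longer sampled, could move the later part of the curves either way.

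The likely size is small: about 0.3 to 0.8 early deaths and, for low and intermediate risk, about 0.1 to 0.3 early AML cases among 20. This assumes constant hazards and Appendix C medians that apply to these subjects. Follow-up runs at least 5 years from first dose, of which 64 days is about 3.5%.

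For HI-E, EE removes essentially only non-responders. The shift depends on an unknown number removed: with six responders and one to five removals, 30.0% becomes 31.6% to 40.0%. A reader might infer that the trial's conclusion is at risk. It is not: the ITT test of at least 6 of 20 stands, and ITT versions of the secondary results will be available. The remaining fault is that the plan asks for two EE curves that add nothing to ITT, and defines EE by an ambiguous word.

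**What to change.** - **Section 9.6.2:** analyse OS in ITT only, and time to AML in ITT and the safety population. Drop EE for both.
- **Section 9.2:** replace *post-treatment* in the EE definition with *after the first dose*.
- **EE rate of HI-E within 24 weeks:** keep it as a supportive figure labelled as conditional on at least 8 weeks of hemoglobin follow-up. Report how many subjects EE removes and why, and state that this rate is not used to claim the Section 9.3 criterion is met.

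Section 9.2 defers detailed inclusion and exclusion rules to the SAP, so the same wording belongs there. The cost is a few sentences, fewer supportive tables and less favourable-looking supportive figures. Sample size, primary test and trial conduct do not change.
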